10.7. Appendix 7: ECG Findings of Potential Clinical Concern

ECG Findings That May Qualify as AEs

Marked sinus bradycardia (rate <40 bpm) lasting minutes.New PR interval prolongation >280 msec.New prolongation of QTcF to >480 msec (absolute) or by \geq60 msec from baseline.New-onset atrial flutter or fibrillation, with controlled ventricular response rate: ie, rate <120 bpm.New-onset type I second-degree (Wenckebach) AV block of >30 seconds' duration.Frequent PVCs, triplets, or short intervals (<30 seconds) of consecutive ventricular complexes.
ECG Findings That May Qualify as SAEs

QTcF prolongation >500 msec.New ST-T changes suggestive of myocardial ischemia.New-onset left bundle branch block (QRS >120 msec).New-onset right bundle branch block (QRS >120 msec).Symptomatic bradycardia.Asystole:
In awake, symptom-free patients in sinus rhythm, with documented periods of asystole \geq3.0 seconds or any escape rate <40 bpm, or with an escape rhythm that is below the AV node;In awake, symptom-free patients with atrial fibrillation and bradycardia with 1 or more pauses of at least 5 seconds or longer;Atrial flutter or fibrillation, with rapid ventricular response rate: rapid = rate >120 bpm.Sustained supraventricular tachycardia (rate >120 bpm) ("sustained" = short duration with relevant symptoms or lasting >1 minute).

- Ventricular rhythms >30 seconds' duration, including idioventricular rhythm (heart rate <40 bpm), accelerated idioventricular rhythm (HR 40 bpm to <100 bpm), and monomorphic/polymorphic ventricular tachycardia (HR >100 bpm (such as torsades de pointes)).
- Type II second-degree (Mobitz II) AV block.
- Complete (third-degree) heart block.

ECG Findings That Qualify as SAEs

- Change in pattern suggestive of new myocardial infarction.
- Sustained ventricular tachyarrhythmias (>30 seconds' duration).
- Second- or third-degree AV block requiring pacemaker placement.
- Asystolic pauses requiring pacemaker placement.
- Atrial flutter or fibrillation with rapid ventricular response requiring cardioversion.
- Ventricular fibrillation/flutter.
- At the discretion of the investigator, any arrhythmia classified as an adverse experience.

The enumerated list of major events of potential clinical concern are recommended as "alerts" or notifications from the core ECG laboratory to the investigator and Pfizer study team, and not to be considered as all inclusive of what to be reported as AEs/SAEs.

10.8. Appendix 8: Permitted and Prohibited Concomitant Medications

The prohibited concomitant medications listed below (Table 4) should not be taken during the C0251008 study.

The Pfizer study team is to be notified of any prohibited medications taken during the study. After consulting with the sponsor, the investigator will make a judgement on the ongoing participation of any participant with prohibited medication use during the study.

This list of drugs prohibited for potential DDI concerns with the IMP may be revised during the course of the study with written notification from the sponsor, to include or exclude specific drugs or drug categories for various reasons (eg, emerging DDI results for the IMP, availability of new information in literature on the DDI potential of other drugs).

This is not an all-inclusive list. Site staff should consult with the sponsor or designee with any questions regarding potential DDI.

Table 4. List of Prohibited and Permitted Concomitant Medications

Medications		C0251008 Treatment Period Day 1-Week 52	C0251008 Follow-up Period
Corticosteroids	Parenteral injections (intra-articular) IA, IM, or IV)	Prohibited	Permitted
	Oral (prednisone or equivalent)	
Permitted (Stage 2)
 
Prednisone \leq15 mg/day or equivalent provided dose is stable for at least 30 days prior to Day 1. 
Permitted (Stage 3)
 
Prednisone \leq20 mg/day or equivalent provided dose is stable for at least 30 days prior to Day 1.Tapering of steroids is permitted after Week 52, in Amended Stage 2 and Stage 3.	Permitted
Immunosuppressive or immunomodulatory agents including methotrexate (MTX), azathioprine (AZA), leflunomide, mycophenolate (including mycophenolate mofetil, mycophenolate mofetil hydrochloride, and mycophenolate sodium), or 6-mercaptopurine (6-MP).		
Permitted
 
Provided pre-existing dose is stable for at least 60 days prior to Day 1.No new immunosuppressives or increase in dose is allowed during the treatment period.Participants can be on 1 of the following cytotoxic agents: MTX, AZA, leflunomide, mycophenolate, or 6-MP, but not on any combination of these cytotoxic agents.	Permitted
Antimalarials (eg, hydroxychloroquine, chloroquine, quinacrine)		
Permitted
 
Provided pre-existing dose is stable for at least 60 days prior to Day 1.	Permitted

Medications	C0251008 Treatment Period Day 1-Week 52	C0251008 Follow-up Period
	
 • No new antimalarial drugs or increase in dose is allowed during the treatment period. 	
Thalidomide, tacrolimus, calcineurin inhibitor or mizoribine	
Prohibited
 
 • Any form of tacrolimus or topical calcineurin inhibitors are not allowed during the treatment period. 	Permitted
Immunosuppressive topical	
Permitted
 
 • Immunosuppressive topical for the scalp. 	Permitted
Immunosuppressive eye drops	Permitted	Permitted
Investigational or marketed biologics (eg, abatacept, tocilizumab, TNF inhibitors)	Prohibited	Prohibited
Cyclophosphamide or chlorambucil	Prohibited	Permitted
Cyclosporine	permitted	Permitted
Other investigational drugs or investigational combinations	Prohibited	Prohibited
B-cell depleting therapy (eg, rituximab, belimumab, epratuzumab)	Prohibited	Prohibited
Any live (live attenuated) vaccines	Prohibited	Prohibited
Inactivated vaccine and boosters	Permitted	Permitted
Kinase inhibitors (eg, tofacitinib, ruxolitinib)	Prohibited	Permitted
IVIG	Permitted	Permitted
Pre- Medication with corticosteroids for IVIG administration: On the day of the IVIG dose administration, pre-medication to prevent hypersensitivity reaction to IVIG is permitted. Steroid dose that was previously used for pre- medication will be permitted (on IVIG dosing day only). After IVIG dosing day, steroid dosing should remain less than or equal to the permitted steroid dosing in the protocol for skin and muscle cohorts.	Permitted	Permitted

Investigators should consult the relevant product label for any other medication used during the study for information regarding medication that is prohibited for concomitant use.

10.9. Appendix 9: Alternative Measures During Public Emergencies

The alternative study measures described in this section are to be followed during public emergencies, including the COVID-19 pandemic. This appendix applies for the duration of the COVID-19 pandemic globally and will become effective for other public emergencies only upon written notification from Pfizer.

Use of these alternative study measures are expected to cease upon the return of business as usual circumstances (including the lifting of any quarantines and travel bans/advisories).

10.9.1. Telehealth Visits (if applicable)

In the event that in-clinic study visits cannot be conducted, every effort should be made to follow up on the safety of study participants at scheduled visits per the [Schedule of Activities](#) or unscheduled visits. Telehealth visits may be used to continue to assess participant safety and collect data points. Telehealth includes the exchange of healthcare information and services via telecommunication technologies (eg, audio, video, video-conferencing software) remotely, allowing the participant and the investigator to communicate on aspects of clinical care, including medical advice, reminders, education, and safety monitoring. The following assessments must be performed during a telehealth visit:

- Review and record any AEs and SAEs since the last contact. Refer to [Section 8.3](#).
- Review and record any new concomitant medications or changes in concomitant medications since the last contact.
- Review and record contraceptive method and results of pregnancy testing. Confirm that the participant is adhering to the contraception method(s) required in the protocol. Refer to [Appendix 4](#) and [Section 1.3](#) of this appendix regarding pregnancy tests.

Study participants must be reminded to promptly notify site staff about any change in their health status.

10.9.2. Alternative Facilities for Safety Assessments

10.9.2.1. Laboratory Testing (if applicable)

If a study participant is unable to visit the site for protocol-specified safety laboratory evaluations, testing may be conducted at a local laboratory if permitted by local regulations. The local laboratory may be a standalone institution or within a hospital. The following safety laboratory evaluations may be performed at a local laboratory:

Please refer to [Table 3](#) of the protocol; not all laboratory collections may be possible.

- Hematology;
- Chemistry;

- Urinalysis;
- Pregnancy testing (if applicable);
- PK (if applicable).

If a local laboratory is used, qualified study site personnel must order, receive, and review results. Site staff must collect the local laboratory reference ranges and certifications/ accreditations for filing at the site. Laboratory test results are to be provided to the site staff as soon as possible. The local laboratory reports should be filed in the participant's source documents/medical records. Relevant data from the local laboratory report should be recorded on the CRF.

If a participant requiring pregnancy testing cannot visit a local laboratory for pregnancy testing, a home urine pregnancy testing kit with a sensitivity of at least 25 mIU/mL may be used by the participant to perform the test at home, if compliant with local regulatory requirements. The pregnancy test outcome should be documented in the participant's source documents/medical records and relevant data recorded on the CRF. Confirm that the participant is adhering to the contraception method(s) required in the protocol.

10.9.2.2. Electrocardiograms

If the participant is unable to visit the study site for ECGs, the participant may visit an alternative facility to have the ECGs performed. Qualified study site personnel must order, receive, and review results.

10.9.3. Home Health Visits

A home health care service may be utilized to facilitate scheduled visits per the [Schedule of Activities](#). Home health visits include a healthcare provider conducting an in-person study visit at the participant's location, rather than an in-person study visit at the site. The following may be performed during a home health visit:

- Lab collection;
- Physical assessment;
- Vital signs.

10.9.4. Adverse Events and Serious Adverse Events

If a participant has COVID-19 during the study, this should be reported as an AE or serious SAE and appropriate medical intervention provided. There is a potential risk of increased susceptibility to viral infections with IFN β blockade as with any antagonist of Type 1 interferon signaling (eg, anti-IFNAR1, anti-IFN α , JAK inhibitors). Viral monitoring will be conducted as a precautionary measure to ensure participant safety. Details can be found in the trial protocol as well as the investigators brochure. Temporary discontinuation of the

study intervention may be medically appropriate until the participant has recovered from COVID-19.

It is recommended that the investigator discuss temporary or permanent discontinuation of study intervention with the study medical monitor.

10.10. Appendix 10: Guidelines for Participant Safety Monitoring and Discontinuation

These guidelines for participant safety monitoring and discontinuation are to be applied to all participants in Study C0251008.

Additional individual participant monitoring is at the discretion of the investigator and dependent on any perceived safety concerns. Unscheduled clinical labs may be obtained at any time during the study to assess such concerns, and a participant may be withdrawn at any time at the discretion of the investigator. For participants on permitted concomitant IVIG, see [Section 8.4.3](#) for specified analyses to be performed at unscheduled visits.

10.10.1. Monitoring

Please Note: For Participants with DM who experience elevated AST, ALT, LDH, Aldolase, and CK, due to muscle involvement the investigator should determine whether or not these are related to the existing condition of DM or if these lab abnormalities are related to another condition. If related to DM, GGT should be <1.5 ULN. Information should be provided in the source documentation with rationale related to any lab abnormalities.

The following laboratory abnormalities require re-testing within 1 week:

- Any single AST and/or ALT elevation ≥ 3 times the upper limit of normal (repeat laboratory testing should include albumin, creatine kinase, total bilirubin, direct and indirect bilirubin, GGT, PT with INR, and alkaline phosphatase), regardless of the total bilirubin. Please note that 3 times the upper limit of normal increases in ALT, AST need confirmation on separate blood draw before undertaking thorough evaluation for liver injury (See [Appendix 6](#) for suggested actions and follow-up assessments in the event of potential drug-induced liver injury);
- For women of child-bearing potential with any positive urine β -hCG test, the participant will have study intervention interrupted and a serum sample submitted to the central laboratory for β -hCG testing.

10.10.2. Discontinuation

Investigators are encouraged to discuss with the sponsor's clinical team as soon as possible, and participants are to be discontinued from treatment if any of the following occur during the study:

- Potential Cases of Decreased eGFR
 - If an individual participant demonstrates CONCOMITANT SCr-based AND serum Cystatin C-based eGFR decline of $\geq 30\%$ compared to the participant's baseline eGFR, then the participant should not be further dosed and adequate, immediate, supportive measures including immediate evaluation by a nephrologist (preferably within 24 hours) with appropriate management and treatment as clinically indicated. Results should be repeated as indicated by the

nephrologist or weekly at a minimum until the eGFR returns to baseline $\pm 15\%$, or the renal parameters are deemed to be stable by the nephrologist and/or the investigator.

- If the participant cannot be seen by a nephrologist within 24 hours (as described above), then the participant should be sent to a local emergency room for evaluation and treatment as clinically indicated.
- Follow-up evaluations should include laboratory tests, detailed history, and physical assessment. In addition to repeating SCr and serum cystatin C, laboratory tests should also include: serum BUN, serum CK, serum electrolytes (including at a minimum potassium, sodium, phosphate/phosphorus, calcium), in addition to urine dipstick, urine microscopic examination, and urinary indices. All cases confirmed on repeat testing as meeting the laboratory criteria for acute kidney injury, with no other cause(s) of laboratory abnormalities identified should be considered as potential cases of drug-induced kidney injury irrespective of availability of all the results of the investigations performed to determine etiology of the abnormal SCr.
- All relevant test results will be forwarded to Sponsor Medical Monitor for review immediately upon receipt by the PI.
- Serious infections defined as any infection (viral, bacterial, and fungal) requiring parenteral antimicrobial therapy, hospitalization for treatment, or meeting other criteria that require the infection to be classified as serious adverse event;
- Other serious or severe AEs, at the discretion of the investigator or sponsor;
- If there are “yes” answers on items 4, 5, or on any behavior question of the C-SSRS, the participant will be discontinued from treatment and referred to a mental health professional for appropriate evaluation and treatment (if the participant cannot be seen by a mental health professional within 24 hours, then the participant should be sent to a local emergency room for psychiatric assessment);
- All of the following laboratory abnormalities require discontinuation if they are confirmed (confirmation through re-testing is expected to occur within 1 week):
 - Two sequential AST or ALT elevation ≥ 3 times the upper limit of normal with at least one total bilirubin value ≥ 2 times the upper limit of normal;^a
 - Two sequential AST or ALT elevation ≥ 3 times the upper limit of normal accompanied by signs or symptoms consistent with hepatic injury;^a
 - Two sequential AST or ALT elevation ≥ 5 times the upper limit of normal, regardless of total bilirubin or accompanying signs or symptoms;^a

- Female participants found to be pregnant during the study;
- Other serious or severe AEs, after consultation with the Pfizer medical monitor or designee.
 - a. In each case, there is a need for additional investigations, such as review of ethanol, recreational drug and dietary supplement consumption; testing for acute hepatitis A, B or C infection and biliary tract imaging should be promptly discussed with the Pfizer medical monitor or designee.
- Use of prohibited medications require participant discontinuation as reflected in [Section 6.8.1](#) and [Appendix 8 \(Section 10.8\)](#) for prohibited medication listing.
- A participant who meets either bulleted criterion based on repeat ECG readings will be withdrawn from the study intervention.
 - QTcF >500 msec.
 - Change from baseline: QTcF >60 msec and QTcF >450 msec.

If a clinically significant finding is identified (including, but not limited to, changes from baseline in QTcF after enrollment), the investigator or qualified designee will determine if the participant can continue in the study and if any change in participant management is needed. This review of the ECG printed at the time of collection must be documented. Any new clinically relevant finding should be reported as an AE. See [Appendix 7 \(Section 10.7\)](#) for further details regarding ECG findings of potential clinical concern.

- Lack of efficacy will be the discretion of the investigator (see rescue medication guidance, [Section 6.8.4](#)).

Any participant meeting discontinuation criteria must enter follow-up with their first follow-up visit occurring 1 week after their last dose whenever possible, until the event has returned to normal or baseline levels or is deemed clinically stable. The procedures scheduled for the early withdrawal visit will be performed on the last day the participant takes the study intervention or as soon as possible thereafter. The only exception to this is when a participant specifically withdraws consent for any further contact with him/her or persons previously authorized by the participant to provide this information.

Participants will be followed post drug discontinuation for 5 terminal half-lives. Additional follow-up visits may occur as needed until any clinically relevant abnormalities or adverse events have resolved, returned to a baseline state, or are deemed clinically stable.

10.11. Appendix 11: Corticosteroid Suggested Taper and Rescue Guidance

10.11.1. Corticosteroid Suggested Taper

The following protocol recommended corticosteroid taper is provided as a guide only. Corticosteroid tapering is ultimately based upon investigator discretion.

The protocol recommended corticosteroid taper is suggested to be started after Week 4 of the C0251008 study. It is also suggested that no corticosteroid tapering occurs between Week 44 and Week 52 due to final assessments being completed. All doses are in prednisone equivalent.

Recommended Oral Prednisone Taper (all doses are approximate as these are examples only):

- **Prednisone dose of 15-20 mg:**
 - Decrease by 2.5 mg every 4 weeks. If starting dose is 19 or 18 mg, then first decrease will be to 17.5 mg a day. If starting dose is 16 or 17 mg, then first decrease will be to 15 mg a day.
- **Prednisone dose of 10-15 mg**
 - Decrease by 2.5 mg every 4 weeks. If starting dose is 13 or 14 mg, then first decrease will be to 12.5 mg. If starting dose is 11 or 12 mg, then first decrease will be to 10 mg.
- **Prednisone dose of 5-10 mg:**
 - Decrease by 1 mg every 2 weeks. If starting dose is 7.5 mg, then first decrease will be to 7 mg.
- **Prednisone dose of 5 mg or less:**
 - No taper is recommended, but prednisone dose can be tapered as per the investigator.

10.11.2. Corticosteroid Rescue Guidance

10.11.2.1. Oral or Intramuscular Corticosteroid Rescue Recommended Guidance for Dermatomyositis Related Reasons

Systemic corticosteroids may be increased as clinically required; however, are suggested to remain within the following stipulations as a guidance.

Recommended Oral or Intramuscular corticosteroid rescue therapy:

- Two of the following options, or the same option used twice are allowed at any time, except between Week 44 and Week 52 due to final assessments being completed.
- Each event of corticosteroid rescue is recommended to be recorded on the concomitant medication pages (All doses are approximate as these are examples only):
 1. Increase in oral corticosteroid dose up to the participant's baseline dose (dose at Day 1). Consideration can then be given to following the protocol driven corticosteroid recommended taper.
 2. Increase in oral corticosteroid dose up to 20 mg of prednisone equivalent per day. Consideration can then be given to following the protocol driven corticosteroid recommended taper.
 3. Oral corticosteroid taper of 20 mg prednisone equivalent per day of over 1 month can be given on top of the baseline corticosteroid dose.

Recommended taper on top of the baseline dose as follows: 20 mg prednisone equivalent per day for 1 week, then 15 mg per day for 1 week, then 10 mg per day for 1 week, then 5 mg per day for 1 week, then back to baseline corticosteroid dose. Consideration can then be given to following the protocol driven corticosteroid recommended taper.

4. An intramuscular injection of approximately 40 mg Depo-Medrol (methylprednisolone acetate suspension [50 mg prednisone equivalent]) as an example. Consideration can then be given to following the protocol driven corticosteroid recommended taper.

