6.1.1.2. Pre-Medication Use on the Day of IVIG Administration

For participants who enroll in the study who are receiving IVIG: On the day of IVIG dose administration, pre-medication to prevent hypersensitivity reaction to IVIG is permitted. The steroid dose that was previously used for pre-medication will be permitted (on IVIG dosing day only). After IVIG dosing day, steroid dosing should remain less than or equal to 15 mg or equivalent of prednisone per day for participants in the severe skin disease cohort and 20 mg or equivalent of prednisone per day for participants in the moderate muscle disease cohort as per protocol [Section 6.8.3](#).

There is no need to change the IVIG dosing schedule or adjust the IVIG dosing schedule related to study intervention administration.

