6.8.3.1. Guidance for Investigators

During the course of the study, those participants who experience a severe flare requiring new or increased doses of immunosuppressants (including new or increased doses of corticosteroids beyond what is permitted), will be discontinued from the treatment period of the study and placed in the follow up period, and therefore, will receive no further study intervention. Rescue therapy may be administered as clinically necessary.

See [Appendix 11 \(Section 10.11\)](#) for further guidelines for corticosteroid use.

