6.8.4. Rescue Medicine

If the participant requires the addition of higher DMARD doses or an additional DMARD for a flare or persistent increase in dermatomyositis activity, then the participant should be discontinued from the treatment period but complete the follow-up visits. High dose oral corticosteroids (>100 mg/day prednisone, or equivalent) or pulse IV doses, or any IV or IM steroid injection would exclude the participant for further treatment in the study.

See [Appendix 11 \(Section 10.11\)](#) for further guidelines for rescue medication.

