10.11.2.2. Corticosteroid Rescue Guidance for Non-Dermatomyositis Reasons

Non-DM reasons may include, for example, poison ivy, or asthma exacerbation.

For example, prednisone equivalent dose of 60 mg or less for 10 days or less. However, this is recommended to be avoided between Week 44 and Week 52 due to final assessments being completed. If corticosteroids for non-dermatomyositis reasons are needed within 4 weeks of the final trial visit, then efficacy assessments will be conducted at the first follow-up visit, such that it is as approximate to 4 weeks after the corticosteroid rescue.

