#### 6.1.1.1. Sensitivity/Supplementary Analyses

### 6.2. Secondary Endpoint(s)

#### 6.2.1. CDASI Activity and Damage Scores

##### 6.2.1.1. Main Analysis

- Estimand strategy: E1.

- Analysis sets: Skin Analysis Set and Muscle Analysis Set.
- Analysis methodology: Each CDASI endpoint (including CFB CDASI activity score, CFB CDASI damage score, absolute value of CDASI activity score, and absolute value of CDASI damage score) will be analyzed using LANCOVA including data from baseline to Week 52 with week as a fixed effect and baseline score as a covariate and an unstructured covariance matrix ([Section 5.2.1](#)).
- Intercurrent events and missing data: Data after study drug discontinuation will be excluded; intermediate missing values will not be imputed.
- The sample size, mean, standard deviation, median, minimum, and maximum at the baseline and postbaseline visits for observed CDASI scores and change from baseline CDASI scores will be presented for each cohort for each CDASI endpoint.
- For each CDASI endpoint, the least-squares (LS) means and the 90% confidence interval for the LS means will be presented and plotted for all postbaseline visits.

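### For a dermatomyositis flare, three oral corticosteroid limits compete with no stated order, so the same dose can be read as ending study treatment or as allowed rescue

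*Protocol*

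**What the plan says.** Four parts of the protocol bear on oral steroids for a DM flare.

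- **Cohort limits.** Table 4 (Appendix 8), in the column for Day 1 to Week 52, permits oral prednisone up to 15 for Stage 2 and up to 20 for Stage 3, each given as "mg/day or equivalent provided dose is stable for at least 30 days prior to Day 1". Section 6.1.1.2, on IVIG pre-medication, repeats both figures as limits during treatment. For the skin cohort, once the IVIG infusion is over, it states: "steroid dosing should remain less than or equal to 15 mg or equivalent of prednisone per day for participants in the severe skin disease cohort". Its figure for muscle participants is 20 mg.
- **Stopping rule.** Section 6.8.3.1 discontinues participants from the treatment period if a severe flare requires immunosuppressant increases, including "new or increased doses of corticosteroids beyond what is permitted".
- **Rescue options.** Section 10.11.2.1 (Appendix 11) allows an oral increase up to 20 mg/day, with no distinction by cohort, or the following: "Oral corticosteroid taper of 20 mg prednisone equivalent per day of over 1 month can be given on top of the baseline corticosteroid dose". Two options, or one option twice, may be used, except between Week 44 and Week 52. The text is labelled guidance and the doses approximate.
- **Exclusion dose.** Section 6.8.4 names "High dose oral corticosteroids (>100 mg/day prednisone, or equivalent" as a reason for no further study treatment.

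On the data side, protocol Section 9.1.1.2 censors measurements taken after withdrawal from treatment. SAP Section 6.2.1.1 says "Data after study drug discontinuation will be excluded", and SAP Sections 6.2.2.1 and 6.2.3.1 apply the same rule to TIS and the core set measures.

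**The concern.** The stopping rule turns on the word permitted, and the protocol has two candidates for its meaning. If Table 4 defines it, a rescue dose offered in Appendix 11 can itself trigger discontinuation. If Appendix 11 defines it, the same dose is ordinary rescue and dosing continues. The exclusion dose in Section 6.8.4 is far above both and does not settle the matter.

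Two things are at stake. One is whether a participant with a severe flare keeps receiving study drug, which could differ between sites for an identical event. The other is which visits enter estimands E1 and E2. A participant who stops loses all later efficacy data. The missing-at-random model then in effect predicts those visits from the participant's earlier values and from those who stayed. A participant who continues contributes every later visit unadjusted, because steroid rescue is not named as an intercurrent event. No sensitivity or supportive analysis in SAP Sections 6.2.1.2, 6.2.2.2 or 6.2.3.2 addresses rescue, and SAP Section 6.5.4 only lists concomitant medications.

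**Working it through.** The plan states no figure to reproduce. The check is simple arithmetic on its doses, followed by a side-by-side reading.

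**Inputs.** Cohort limits 15 mg/day (skin) and 20 mg/day (muscle): Table 4 and Section 6.1.1.2. On-top taper of 20, 15, 10, then 5 mg/day, one week each: Section 10.11.2.1, option 3. Increase up to 20 mg/day: same section, option 2. Exclusion above 100 mg/day: Section 6.8.4.

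**On-top option.** Weekly total = baseline dose + (20, 15, 10, 5).

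| Cohort (limit) | Baseline, mg/day | Weekly totals, mg/day | Weeks above the Table 4 limit |
|---|---|---|---|
| Skin (15) | 0 | 20, 15, 10, 5 | 1 of 4 |
| Skin (15) | 5 | 25, 20, 15, 10 | 2 of 4 |
| Skin (15) | 10 | 30, 25, 20, 15 | 3 of 4 |
| Skin (15) | 15 | 35, 30, 25, 20 | 4 of 4 |
| Muscle (20) | 0 | 20, 15, 10, 5 | 0 of 4 |
| Muscle (20) | 5 | 25, 20, 15, 10 | 1 of 4 |
| Muscle (20) | 10 | 30, 25, 20, 15 | 2 of 4 |
| Muscle (20) | 15 | 35, 30, 25, 20 | 3 of 4 |
| Muscle (20) | 20 | 40, 35, 30, 25 | 4 of 4 |

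At the maximum baseline, the first-week dose is 35/15 = 2.3 times the skin limit and 40/20 = 2.0 times the muscle limit. No total approaches 100 mg/day.

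**Option 2.** 20 mg/day exceeds the skin limit of 15 but not the muscle limit of 20.

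**One event, three readings.** Take a skin participant on 15 mg/day with a severe flare at Week 20 who uses the on-top option.

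- Table 4 with Section 6.8.3.1: 35 exceeds 15, so treatment ends. As the Schedule of Activities reads, the later on-treatment CDASI assessments at Weeks 24, 36, 48 and 52 leave the analysis.
- Section 10.11.2.1: the dose is an allowed option. It returns to 15 mg/day after four weeks, about Week 24, and all four assessments stay in.
- Section 6.8.4: 35 is below 100, so no exclusion follows.

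**Zones of dose for a DM flare.** Above 15 (skin) or 20 (muscle) and up to 35 or 40 mg/day, a dose can be over Table 4, inside Appendix 11 and below the Section 6.8.4 figure. From there to 100 mg/day it is outside the suggested options but still not named as excluded in Section 6.8.4.

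**The case against.** The best defence is that the sections do point somewhere. Section 6.8.3 opens by referring to Appendix 11, and Sections 6.8.3.1 and 6.8.4 both close with the same reference. Section 6.8.3 also leaves steroid increases to the investigator. The requirement in Table 4 for a stable dose over 30 days before Day 1 reads like a condition on background therapy. On this view, permitted means what Appendix 11 permits, and nothing conflicts.

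That reading is reasonable, but the text does not establish it. The Table 4 column covers Day 1 to Week 52. Section 6.1.1.2 applies 15 and 20 mg/day as limits during treatment, and the IVIG row of Table 4 speaks of permitted dosing by cohort, whereas the Appendix 11 rescue options make no cohort distinction. Section 6.1.1.2 cites Section 6.8.3 for its limits, but that section gives no dose. Appendix 11 is suggested guidance with approximate doses, which is a weak boundary for a mandatory stopping rule.

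Other parts of the defence stand. The stopping rule covers only a severe flare, so milder flares may fall outside it. DM rescue is barred between Week 44 and Week 52, so a completed on-top taper does not overlap the Week 52 assessment if the guidance is followed. Option 2 has no stated end, so a sustained increase could carry over. Efficacy is secondary, with no hypothesis tests or p-values.

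A reader might also count five conflicting ceilings: 15, 20, 35 to 40, 60 and 100 mg/day. The documents do not support that count. The 15 and 20 mg figures belong to different cohorts. The range 35 to 40 is derived at maximum baseline, not stated. The 60 mg figure in Section 10.11.2.2 ("prednisone equivalent dose of 60 mg or less for 10 days or less") is an example for non-DM reasons such as asthma.

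**Conclusion.** The contradiction is real in narrower form. For a severe DM flare, three oral statements compete with no stated order: the cohort limit, the Appendix 11 options and the exclusion above 100 mg/day. The same dose can be read as ending study treatment or as allowed rescue.

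Its size can be given in dose only: first-week totals up to 35 mg/day against a limit of 15, or 40 against 20, assuming the maximum permitted baseline and the approximate Appendix 11 schedule. It cannot be given in participants. A reader might attach a percentage of each cohort censored under one reading and not the other, but any such figure would need an assumed rescue rate and an assumed split of the roughly 30 participants; the documents give neither. A reader might also infer that Week 52 values are generally obtained under raised steroids. The Week 44 to Week 52 bar argues against that.

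The effect falls mainly on continued treatment and on which post-rescue visits, Week 52 included, enter the descriptive secondary estimates.

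**What to change.** **Protocol.** Reconcile Table 4, 6.1.1.2, 6.8.3.1, 6.8.4 and 10.11.2.1 so that permitted has one meaning and one consequence per cohort, and have each section cite that rule. The content is for the sponsor's clinicians; no dose or rule is proposed here. The same amendment should reconcile the intramuscular route, which Section 10.11.2.1 option 4 allows, Table 4 prohibits during treatment, and Section 6.8.4 treats as a reason for exclusion.

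**SAP.** Use the separate oral corticosteroid CRF described in Section 6.8.3 to flag visits during or after oral rescue above the reconciled limit. Add a supportive summary of CDASI and TIS with and without those visits.

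**Cost.** A wording amendment, possible retraining at some sites, and one supportive table from data already being collected.
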